	2. [Dose Escalation Phase] Histologically or cytologically confirmed diagnosis of gastric lung
	colorectal or breast cancer on file
	[Cohort Expansion Phase]
	Histologically or cytologically confirmed diagnosis of Globo H-positive NSCLC
	3. [Dose Escalation Phase] Subjects with recurrent or metastatic incurable discoses that failed to
	Subjects with recurrent of metastatic incurable disease that falled to

	respond to at least one line of anticancer standard therapy and for which	
	standard treatment is no longer effective or tolerable.	
	[Cohort Expansion Phase]	
	Subjects with metastatic NSCLC who have achieved stable disease (SD),	
	or partial response (PR) status after at least 1 regimen of anticancer	
	therapy (i.e., chemotherapy, or targeted therapy, or PD-1/PD-L1	
	antagonists either alone or in combination), and there are no standard	
	treatments available except permitted Target or PD-1/PD-L1 therapies as	
	listed in section 7.1 (i.e., add on with ongoing first line Targeted therapy	
	or PD-1/PD-L1 therapy).	
4	4. Measurable disease (i.e., present with at least one measurable lesion per	
	RECIST, version 1.1 [Eisenhauer 2009]).	
5	. [Dose Escalation Phase]	
	No known central nervous system (CNS) metastases or neurological	
	symptoms possibly related to active CNS metastasis in Dose Escalation	
	Phase.	
	[Cohort Expansion Phase]	
	Subjects with asymptomatic CNS metastases for at least four weeks	
	before study drug treatment	
(5. Performance status: $ECOG \le 1$	
	7. Organ Function Requirements – Subjects must have adequate organ	
	functions as defined below:	
	- $AST/ALT \leq 3X$ ULN (upper limit of normal)	
	- $AST/ALT \le 5X$ ULN [with underlying liver metastasis]	
	- Total bilirubin $\leq 2.0 \text{ X ULN}$	
	- Serum creatinine ≤ 1.5 X ULN	
	- ANC $\geq 1500 / \mu L$	
	- Platelets $> 100,000/\mu L$	
8	Subjects of child-bearing potential must agree to use acceptable	
	contraceptive methods during treatment and until the end of the study.	
	Subject not of childbearing potential (i.e., permanently sterilized,	
	postmenopausal) can be included in study. Postmenopausal is defined	
	as 12 months with no menses without an alternative medical cause.	
9	9. Ability to understand and the willingness to sign a written informed	
	consent document according to institutional guidelines.	
Selection Criteria:	Exclusion Criteria	
1	Patients who have not received standard chemotherapy, hormonal or	

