3 ELIGIBILITY CRITERIA

3.1 Inclusion Criteria

- 1. Subjects \geq 21 years of age
- 2. [Dose Escalation Phase]

Histologically or cytologically confirmed diagnosis of gastric, lung, colorectal or breast cancer on file

[Cohort Expansion Phase]

Histologically or cytologically confirmed diagnosis of Globo H-positive NSCLC

3. [Dose Escalation Phase]

Subjects with recurrent or metastatic incurable disease that failed to respond to at least one line of standard anticancer therapy and for which standard treatment is no longer effective or tolerable.

[Cohort Expansion Phase]

Subjects with metastatic NSCLC who have achieved stable disease (SD), or partial response (PR) status after at least 1 regimen of anticancer therapy (i.e., chemotherapy, or targeted therapy, or PD-1/PD-L1 antagonists either alone or in combination), and there are no standard treatments available except permitted Target or PD-1/PD-L1 therapies as listed in section 7.1 (i.e., add on with first line ongoing Targeted therapy or PD-1/PD-L1 therapy).

- 4. Measurable disease (i.e., present with at least one measurable lesion per RECIST, version 1.1 [Eisenhauer 2009]).
- 5. [Dose Escalation Phase]

No known central nervous system (CNS) metastases or neurological symptoms possibly related to active CNS metastasis in Dose Escalation Phase.

[Cohort Expansion Phase]

Subjects with asymptomatic CNS metastases for at least four weeks before study drug treatment

- 6. Performance status: $ECOG \le 1$
- 7. Organ Function Requirements Subjects must have adequate organ functions as defined below:
 - AST/ALT \leq 3X ULN (upper limit of normal)
 - $AST/ALT \le 5X$ ULN [with underlying liver metastasis]
 - Total bilirubin $\leq 2.0 \text{ X ULN}$
 - Serum creatinine ≤ 1.5 X ULN
 - ANC $\geq 1500 / \mu L$
 - Platelets > $100,000/\mu L$
- 8. Subjects of child-bearing potential must agree to use acceptable contraceptive methods during treatment and until the end of the study. Subject not of childbearing potential (i.e., permanently sterilized, postmenopausal) can be included in study. Postmenopausal is defined as 12 months with no menses without an alternative medical cause.
- 9. Ability to understand and the willingness to sign a written informed consent document according to institutional guidelines.

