For 100 μ g dose cohort (Cohort 3), firstly three subjects will be enrolled in this cohorts. If one out of the first three Cohort 3 subjects develops a DLT, an additional three subjects will be further enrolled. If none of the first three or less than 2 of the 6 subjects experience DLT at the 100 μ g dose level, then this dose will be maximum dose for escalation phase. If more than 1 of 6 subjects experience DLT at this dose level, study will be suspended temperately and DSMB will review safety data to recommend if the study should be de-escalate to 30 μ g to complete a maximum of 6 subjects.

Upon the completion of 5 injections of OBI-833/OBI-821 in subjects in the dose escalation phase, OBI Scientific Committee justified safety, efficacy and immune response data of all the dose escalation phase subjects and recommend 30 µg dose of OBI-833 for cohort expansion.

OBI Scientific Committee also examined the data of all the dose escalation phase subjects and preclinical efficacy data to evaluate the type of cancers to benefit from OBI-833/OBI-821 treatment. OBI Scientific Committee determined that lung cancer (Non-Small Cell Lung Cancer) subjects with SD or PR tumor status are to be enrolled for preliminary antitumor activity evaluation. Up to 14 subjects are to be enrolled in the cohort expansion phase.

The total number of subjects to be enrolled in the study is thus flexible: a maximum number of 18 subjects can be enrolled in the dose escalation phase; and a maximum number of 14 subjects can be enrolled in the cohort expansion phase. A maximum of total 32 subjects can be enrolled in this Phase I study.

Dose modification may be considered, as justified by emerging safety data. Subject tumor biopsy/tissue samples will be collected at Week 1 using fresh prepared or paraffinated material from original surgery specimens to test for expression level of Globo H, SSEA-3, SSEA-4 and PDL-1 for data analysis purpose. IHC data is not for eligibility criteria for Dose Escalation Phase but only Globo-H⁺ NSCLC subjects will be enrolled in Cohort Expansion Phase.

Subjects who are eligible for participation in this study will be enrolled into the dose cohort that is open at the time the subject is registered for enrollment in Dose Escalation Phase.

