- Conduct routine urinalysis pH, protein, glucose, specific gravity, ketone, bilirubin, and urobilinogen. Analysis of urinary sediments (RBC, WBC, epithelial casts, hyaline casts, and bacterial) is optional.
- Conduct hematology test includes hemoglobin, hematocrit, WBC, RBC, platelet, differentials, RF and ESR.
- Conduct serum chemistry analysis includes sodium, potassium, chloride, calcium, magnesium, BUN, creatinine, ALT, AST, alkaline phosphatase, total protein, albumin, total bilirubin, LDH, amylase, lipase, cholesterol, triglycerides, cortisol, T3, T4, free T4, and TSH.
- Conduct HBV (e.g., HBsAg, HBeAg, and if clinically indicated, HBcAb and/or HBV DNA), HCV (e.g., anti-HCV) testing. Conduct HIV testing if no historical data are available. Optional tests (e.g., viral load) can be ordered based on lab test results and Investigator's clinical judgment for suspected active infection on follow-up visits. Antiviral agents are allowed for the treatment and management of viral infections. However, interferon therapy is not allowed, and if indicated, the subject needs to be excluded from the study.
- Perform 12-Lead ECG.
- Perform Tumor Assessment:
 - Full body CT scans (chest, abdomen, and pelvis) will be performed at screening and used as the baseline scan. If full body CT scan has been performed within 4 weeks of the screening exam (the date consent form sign by patient), then this previously performed scan can be used as the baseline scan.
 - To identify and record lesions to be evaluated for response based on RECIST 1.1 criteria.
 - Imaging will be assessed by the study site radiologist or delegated investigators.
 - For cohort expansion phase, an interval of at least 6 weeks is required for Stable Disease (SD) status; an interval of at least 4 weeks is required for Partial Response (PR) status.
- Record use of concomitant medications.
- Perform re-testing of lab assessments: a re-test may be allowed after 1 week (or by Investigators' judgment) from the initial lab test to re-confirm the subject's organ function or condition. However, the assessment needs to be conducted within the specified screening period prior to first dosing of the investigational drug.
- Perform pre-treatment tumor-specific antigen testing: CEA and CYFRA21-1 for all enrolled subjects in selected sites.

• Collect blood samples for exploratory analysis of the B/T cell immunogenomic and Ex vivo immunogenicity analysis in selected Taiwan sites.

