7 TREATMENTS PERMITTED AND PROHIBITED DURING STUDY

7.1 **Permitted Treatments during Study**

[Dose Escalation Phase]

- 1. Analgesics: Non-steroidal anti-inflammatory drugs (NSAID), analgesics other than NSAID (like aspirin), and opiates may be used for pain control.
- 2. GCSF and Hematopoietic growth factors will be allowed in the dose escalation phase if deemed necessary by physicians.
- 3. Antihistamine (H1 and H2) and decongestant: cetirizine HCl, fexofenadine HCl, levocetirizine, and pseudoephedrine.
- 4. Antiemetic and anti-pruritics therapy.
- 5. Therapy with bisphosphonates (e.g., to treat bone metastases), is at the discretion of the investigator.

[Cohort Expansion Phase]

- 1. Analgesics: Non-steroidal anti-inflammatory drugs (NSAID), analgesics other than NSAID (like aspirin), and opiates may be used for pain control.
- 2. Antihistamine (H1 and H2) and decongestant: diphenhydramine, hydroxyzine, cimetidine, ranitidine, famotidine, cetirizine HCl, fexofenadine HCl, levocetirizine, and pseudoephedrine.
- 3. Antiemetic (eg., ondansetron) and anti-pruritics (eg., diphenhydramine or hydroxyzine) therapy.
- 4. Therapy with bisphosphonates (e.g., to treat bone metastases), is at the discretion of the investigator.
- 5. EGFR/ALK TKIs (e.g., gefitinib, erlotinib, afatinib and crizotinib), EGFR mAb (Necitumumab), bevacizumab and PD-1/PD-L1 inhibitors (e.g., pembrolizumab and nivolumab)

7.2 **Prohibited Treatments during Study**

The following treatments are prohibited during the Treatment and Post-treatment periods of the study until End of Study (Appendix II):

[Dose Escalation Phase]

- 1. Anti-cancer treatment: no other anti-cancer therapy is allowed during the study. The list of other chemotherapy agents, chemotherapeutic agents, active or passive immunotherapy, includes, but is not limited to:
 - Chemotherapeutic agents: antimetabolites, alkylating agents, vinca alkaloid, epipodophyllotoxins, taxanes, camptothecins, antitumor antibiotics, nitrosoureas folate analogue metabolic inhibitor, and miscellaneous cytotoxic agents.
 - Surgery
 - Radiotherapy
- 2. Biologic Agents: Monoclonal antibodies, Interferons and Interleukins
- 3. Immunotherapy: cyclosporin, rapamycin, tacrolimus, rituximab, alemtuzumab, natalizumab etc.

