- 4. Steroids: iv/oral steroids except single prophylactic use in CT/MRI scan or other one-time use in approved indications. The interval between iv/oral steroids administration and first dose of OBI-833/OBI-821 must be more than pharmacological duration or 5 half-lives of administered steroids whichever is the longer.
 - Uses of inhaled and topical steroids are allowed.
- 5. Tyrosine kinase inhibitors
- 6. Alternative and complementary medicine may affect immune system
- 7. Other investigational drugs

[Cohort Expansion Phase]

- 1. Anti-cancer treatment: The list of chemotherapy agents, active or passive immunotherapy (Appendix II), includes, but is not limited to:
 - Chemotherapeutic agents: antimetabolites, alkylating agents, vinca alkaloid, epipodophyllotoxins, taxanes, camptothecins, antitumor antibiotics, nitrosoureas folate analogue metabolic inhibitor, and miscellaneous cytotoxic agents. EGFR/ALK TKIs are permitted.
 - Surgery
 - Radiotherapy
- 2. Biologic Agents: Interferons, Interleukins, Denosumab (RANKL inhibitor), GCSF and Hematopoietic growth factors
- 3. Immunotherapy: cyclosporin, rapamycin, tacrolimus, rituximab, alemtuzumab, natalizumab, cyclophosphamide, etc (except PD-1/PD-L1 antagonists).
- 4. Steroids: iv/oral steroids except single prophylactic use in CT/MRI scan or other one-time use in approved indications. The interval between iv/oral steroids administration and first dose of OBI-833/OBI-821 must be more than pharmacological duration or 5 half-lives of administered steroids whichever is the longer.
 - Topical (except injection sites) and inhaled steroid use is allowed

- 5. Alternative and complementary medicine may affect immune system.
- 6. Other investigational drugs

7. Subjects who continuous treatment after disease progression are allowed to concomitant use of all approved anti-cancer therapies

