12.4 Statistical Methods

12.4.1 Analytical Sets

• The Safety Population is the group of subjects who received at least one dose of investigational product and had at least one post-dose safety assessment.

- The Immune Response Population is the group of subjects who received at least one dose of investigational product and had anti-Globo H IgG or IgM production.
- The Tumor Response Population will include all enrolled subjects.
- 12.4.2 Premature Termination and Missing Values

All available data will be displayed and utilized in data analysis. Subjects prematurely terminating the study treatment will be summarized. Listings of subjects with premature termination will be provided with the dates and reasons for termination. Missing data will not be replaced by any estimated or imputed values.

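### Expansion-phase Section 7.1 permits active targeted and PD-1/PD-L1 drugs without the ongoing-at-entry limit in inclusion 3, so a response to a newly started drug would count in the OBI-833 cohort

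*Protocol*

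**What the plan says.** **Entry.** Inclusion 3 for the expansion phase (Section 3.1, repeated in the Synopsis) requires stable disease "or partial response (PR) status after at least 1 regimen of anticancer therapy (i.e., chemotherapy, or targeted therapy, or PD-1/PD-L1 antagonists", alone or combined. No standard treatment may remain other than the therapies permitted in Section 7.1. The criterion explains that exception as "add on with first line ongoing Targeted therapy or PD-1/PD-L1 therapy".

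**Conduct.** Section 7.1, expansion item 5, permits "EGFR/ALK TKIs (e.g., gefitinib, erlotinib, afatinib and crizotinib), EGFR mAb (Necitumumab), bevacizumab and PD-1/PD-L1 inhibitors (e.g., pembrolizumab and nivolumab"). It sets no condition on start date, line of therapy or stability of the regimen. The expansion list in Section 7.2 adds that "EGFR/ALK TKIs are permitted" and exempts PD-1/PD-L1 antagonists from the immunotherapy prohibition. Appendix II exempts necitumumab and bevacizumab. None of these exemptions is qualified. Exclusion 8 (Section 3.2) also releases the Section 7.1 therapies from its 4-week washout.

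**Endpoint.** Tumour response by RECIST 1.1 is a secondary endpoint (Section 9.2). Partial response is a fall of at least 30% from the baseline sum of diameters, whatever else the subject is taking (Section 10.3). On the analysis set, Section 12.4.1 says: "The Tumor Response Population will include all enrolled subjects". Section 12.4.2 uses all available data. Section 4.1 gives the purpose of the cohort: these subjects "are to be enrolled for preliminary antitumor activity evaluation".

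**The concern.** Inclusion 3 conveys a cohort in which OBI-833 is added to a drug the subject is already taking, or given where no standard option remains. The rules that govern the subject after entry do not preserve that picture. If a listed drug with activity of its own is started before progression and the tumour then shrinks, the shrinkage is measured from the OBI-833 baseline and enters the response rate of a single-arm cohort of at most 14.

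The error runs towards more apparent activity. What is at stake is the reading of the cohort's response rate as a preliminary activity signal. The point concerns only the period before progression. Section 7.2 deals separately with subjects who continue injections after progression and opens all approved anti-cancer therapies to them.

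**Working it through.** **Inputs from the protocol.** There are 3 dose cohorts of at most 6 subjects, and at most 14 expansion subjects (Sections 4.1 and 12.2). The plan's own total reproduces: 3 × 6 = 18, and 18 + 14 = 32. The plan states no response rate, power or alpha, so there is no further figure to reproduce.

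**Text check: can a listed drug be started before progression, and would the response count?**

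1. Is it prohibited? No. Section 7.1 permits it, and Section 7.2 and Appendix II exempt it. In the escalation phase, Section 7.2 rules out any other anti-cancer therapy during the study. The matching expansion item does not repeat that statement.
2. Is the subject taken off treatment? No. Section 11.1 does not list the start of a new anti-cancer drug. Using a permitted drug is not noncompliance.
3. Who could do it? A subject on one listed drug could switch to another or add a second. A subject whose qualifying regimen was chemotherapy alone could enter with no background drug and later start a listed one. How far this second route is open depends on how inclusion 3 is read (see the objection).
4. Is the later scan left out? Nothing in Sections 10.3, 12.4.1 or 12.4.2 sets it aside.

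**Size.** Each response adds 1/14 = 7.1 points. Exact 95% confidence intervals are 0% to 23.2% for 0/14, and 0.2% to 33.9% for 1/14 = 7.1%.

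Two quantities are assumptions, because the protocol gives neither: the number k of subjects who start a listed drug before progression, and the probability p of response to that drug. The chance of at least one such response is 1 − (1 − p)^k. The mean addition to the response rate is k × p / 14.

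| k | p = 10%: chance | p = 60%: chance | Mean addition, p = 10% to 60% |
|---|---|---|---|
| 1 | 10% | 60% | 0.7 to 4.3 points |
| 2 | 1 − 0.9² = 19% | 1 − 0.4² = 84% | 1.4 to 8.6 points |
| 3 | 1 − 0.9³ = 27% | 1 − 0.4³ = 94% | 2.1 to 12.9 points |
| 4 | 1 − 0.9⁴ = 34% | 1 − 0.4⁴ = 97% | 2.9 to 17.1 points |

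With no starters the effect is zero.

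**The case against.** Several objections are sound and set the limits of the point.

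- **Not a flat contradiction.** A reader might infer that Sections 3.1 and 7.1 contradict each other. They do not: inclusion 3 governs entry and Section 7.1 governs conduct. The fault is an entry limit that is not carried forward. Section 7.2 opens all approved therapies only after progression, which suggests that new lines were expected there. Nothing states that limit for the listed drugs before progression.
- **The post-chemotherapy route may be narrow.** Take a subject who enters after chemotherapy, with a PD-1 inhibitor available but not in use. Read strictly, inclusion 3 excludes that subject, because a standard option remains that is not ongoing first-line therapy. What then remains is starting a listed drug that is not a standard option for the subject. Switching or adding a drug during an ongoing listed therapy is open on either reading.
- **Counting is inferred.** No sentence says that scans after a new drug count. This follows from the RECIST definition, the all-enrolled set and the use of all available data. A statistical analysis plan, not shown here, could add a rule. It would not change the permitted-treatment wording, which belongs to the protocol.
- **New starts can be identified.** Concomitant medications are recorded at screening, during treatment and after treatment (Sections 5.1, 5.4 and 5.5). It would be too strong to say that such responses cannot be separated.
- **Run-in is another matter.** A reader might extend the point to drugs ongoing at entry, since "an interval of at least 6 weeks is required for Stable Disease (SD) status" and at least 4 weeks for partial response, so that shrinkage still under way is scored from a new baseline. The documents do not support calling that an error. It is a disclosed feature of an add-on design, shrinkage before entry earns no credit, and reconciling Section 7.1 would not alter it.
- **Limited consequence.** No hypothesis is tested (Section 12.1), the study is described as pilot and exploratory (Section 12.2), and ongoing background drugs already limit attribution. This is true, but a drug started on study is an avoidable further source of confusion.

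**Conclusion.** The point holds as a gap in protocol wording with an effect on interpretation. As written, a subject may add, switch to or start a listed active drug before progression without a deviation, and a resulting response would enter the expansion cohort's tumour-response result. Each one is worth 7.1 points.

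How many would occur is unknown. The 10% to 97% range rests wholly on the assumed 1 to 4 starters and 10% to 60% response rates. A reader might take its upper end as a forecast, but nothing in the protocol supports any particular number of starters. Subjects enter in stable disease or partial response, so four starting a new drug before progression is a high case.

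The endpoint is secondary, descriptive and uncontrolled. Error rates, sample size and the primary safety endpoint are not affected. The change is worth making because it is cheap and removes a bias that favours OBI-833 in the evaluation for which the cohort was opened.

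**What to change.** 1. Reconcile Section 7.1 item 5, the expansion list in Section 7.2 and Appendix II with inclusion 3, so that all say the same about whether the listed drugs must be ongoing at entry. Which clinical rule applies is for the sponsor and investigators; this review does not choose one.
2. Whichever rule is adopted, state that the expansion tumour-response summary uses RECIST assessments up to the start of any new listed anti-cancer drug, and that later assessments are listed separately.
3. Report tumour response separately for subjects with and without background therapy.

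**Cost.** Some protocol wording, plus use of the concomitant-medication dates already collected. A few assessments drop out of the summary, and the reported response rate may be slightly lower. With at most 14 subjects, the two background-therapy groups will be small and suited to description only.

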For each subject in dose escalation phase, maximum of 10 doses of OBI-833 (equivalent to 10, 30 or 100µg of Globo H)/OBI-821 (100µg) will be administered subcutaneously at Weeks 1, 2, 3, 4, 6, 8, 12, 16, 20, and 24 (Visits 1, 2, 3, 4, 5, 6, 7, 8, 9 and 10, respectively). Patients who prematurely withdraw from dose escalation phase will be replaced. To meet the replacement a subject should fulfill the following criteria: 1) Not receives a total of 5 OBI-833/OBI-821 injections, during the dose escalation phase; and 2) Reason of not completing 5 injections is other than development of related adverse event or a DLT (e.g., noncompliance or withdrew of consent).

For Cohort Expansion Phase, patients will be treated subcutaneously at Weeks 1, 2, 3, 4, 6, 8, 12, 16, 20, 24 and every 8 weeks until disease progression, intolerable toxicity, withdrawal of consent, or up to 1 year after the last subject receives the first dose of study treatment. Subjects may continue treatment after disease progression at discretion of the investigator. The following clinical situations should be conformed for continued injection after disease progression (FDA Guidance for Industry, 2011):

- Subjects continue to meet all other study protocol eligibility criteria.
- —All drug-related toxicities resolved to the baseline level.
- No deterioration of subject performance status.
- Does not delay imminent intervention to prevent serious complications of disease progression (e.g., CNS metastases).

For the subjects discontinued treatment because of disease progression, subjects will be continually evaluated for safety and immune response every 8 weeks until the end of the study, which is 24 weeks after the last dose. For the subjects who are eligible and willing to continue injection after disease progression, subjects will be treated with OBI-833/OBI-821 every 8 weeks for additional 3 injections, which is a total of 24 weeks after disease progression, to evaluate clinical and immune responses. Subsequently, subjects will be followed up for survival every 12 weeks up to 24 weeks after End of Study.

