The following evaluations are to be conducted every 4 weeks for Dose Escalation Phase or every 8 weeks for Cohort Expansion Phase until the end of the study ("End of Study"), which is 12 weeks (Dose Escalation Phase) or 24 weeks (Cohort Expansion Phase) after the last subcutaneous dose of the investigational drug.

- Perform physical examination including vital signs (blood pressure, respiratory rate, pulse, and body temperature) and weight.
- Conduct routine urinalysis pH, protein, glucose, specific gravity, ketone, bilirubin, and urobilinogen. Analysis of urinary sediments (RBC, WBC, epithelial casts, hyaline casts, and bacterial) is optional.

- Conduct hematology test includes hemoglobin, hematocrit, WBC, RBC, platelet, differentials, RF and ESR.
- Conduct serum chemistry analysis includes sodium, potassium, chloride, calcium, magnesium, BUN, creatinine, ALT, AST, alkaline phosphatase, total protein, albumin, total bilirubin, LDH, amylase, lipase, cholesterol, triglycerides, cortisol, T3, T4, free T4, and TSH.
- Collect blood samples for measurement of anti-Globo H IgG and IgM titer.
- Collect blood samples for exploratory analysis for the following biomarkers:
 - Monitoring of immune response of anti-Globo H, anti-SSEA-3 and anti-SSEA-4 antibody production.
 - ADCC and CDC
- Collect blood samples for exploratory analysis for the following biomarkers Dose Escalation Phase: Week 28 (Visit 11) or Cohort Expansion Phase: End of study:
 - CTC (only in selected Taiwan sites)
- Collect blood sample for exploratory cellular immune response only if either anti-Globo H, anti-SSEA-3, or anti-SSEA-4 serum concentration reaches 20 µg/ml 4 continue visits prior to administration of investigational drug (8-Week after the last injection; PTP1):
 - T cell and B cell immune response in selected Taiwan sites
- Collect blood samples for exploratory analysis for the following biomarkers— Cohort Expansion Phase: 8 weeks after 1st disease progression:
 - B/T cell immunogenomic analysis (only in selected Taiwan sites)
- Perform tumor assessment according to the RECIST 1.1 criteria at weeks 36 (Visit 13) for Dose Escalation Phase or at every visit for the continuous injection subjects after disease progression in Cohort Expansion Phase. If the data of CT assessment are available within 6 weeks prior to the scheduled visit, the assessment of CT may not be performed based on the investigator's discretion.

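### In Cohort Expansion, subjects who stop OBI-833/OBI-821 at progression are not released from the ban on chemotherapy, radiotherapy and surgery while they stay in post-treatment follow-up

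*Protocol*

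**What the plan says.** Section 7.2 sets the period of the ban for both phases: "The following treatments are prohibited during the Treatment and Post-treatment periods of the study until End of Study". The Cohort Expansion list includes chemotherapeutic agents, surgery and radiotherapy under item 1, and certain biologics under item 2. Item 7 then makes one exception: "Subjects who continuous treatment after disease progression are allowed to concomitant use of all approved anti-cancer therapies". Appendix II repeats it in the same words.

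Section 7.1, item 5, leaves some anti-cancer drugs open to every Cohort Expansion subject: EGFR/ALK TKIs, "EGFR mAb (Necitumumab), bevacizumab and PD-1/PD-L1 inhibitors". Inclusion criterion 3 (Section 3.1) adds that at entry "there are no standard treatments available except permitted Target or PD-1/PD-L1 therapies as listed in section 7.1".

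Section 4.1 keeps subjects who stop in follow-up: "For the subjects discontinued treatment because of disease progression, subjects will be continually evaluated for safety and immune response every 8 weeks", up to End of Study at 24 weeks after the last dose. It also sets conditions for continuing the vaccine, among them "No deterioration of subject performance status" and "Does not delay imminent intervention to prevent serious complications of disease progression".

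**The concern.** The exception follows the wrong variable. It depends on whether the subject keeps taking the vaccine, although the need for new therapy comes from the progression. A subject who fails either Section 4.1 condition just quoted has to stop, and so stays under the ban. A fitter subject who continues may use any approved therapy. Asymptomatic CNS metastases are allowed at entry (inclusion criterion 5), so a later need for radiotherapy or surgery is foreseeable.

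Two things are at stake. The first is patient protection: within the rules, a subject with progressed metastatic NSCLC gets chemotherapy only by accepting more vaccine, if eligible, or by giving up the scheduled visits. The second is data. Safety is the primary endpoint (Section 9.1), anti-Globo H antibody is a secondary endpoint (Section 9.2), and Section 2.6 describes a delayed antibody response, so the late visits matter. Section 9.3 asks for every effort to complete scheduled evaluations even after treatment is withdrawn. The rule works against that aim without contradicting it.

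**Working it through.** The plan states no figure for this point, so the check is a comparison of texts plus the length of the remaining ban.

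**Who is released.** Sections 4.1, 5.5, 5.7, 7.1, 7.2, 11.1, 11.2 and Appendix II contain no sentence that frees a subject who stops at progression and stays in the post-treatment period. Item 7 and its copy cover only those who continue.

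**What item 7 releases.** It speaks of approved anti-cancer therapies and names neither radiotherapy nor surgery. Both stand under the anti-cancer treatment item of Section 7.2, so including them is reasonable but not explicit. Release of approved drugs is the firm part.

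**What the ban could protect.** Section 5.5 schedules post-progression tumour assessment "at every visit for the continuous injection subjects after disease progression in Cohort Expansion Phase", and Table 2, footnote 18, says the same. The subjects still scanned are therefore the ones allowed other therapy. For those who stop, the ban can protect only antibody and safety data.

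**Length of the remaining ban.** Inputs: doses at Weeks 1, 2, 3, 4, 6, 8, 12, 16, 20 and 24, then every 8 weeks (Section 4.1); scans at Weeks 12 and 24, then every 8 weeks, before dosing (Section 5.4); post-treatment visits at 8, 16 and 24 weeks after the final injection, the last being End of Study (Table 2).

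Weeks left = 24 − t, where t is the number of weeks since the last dose.

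| Progression found | Last dose | End of Study | Weeks left | Post-treatment visits |
|---|---|---|---|---|
| Week 12 scan, dose withheld | Week 8 | 8 + 24 = Week 32 | 24 − 4 = 20 | Weeks 16, 24, 32 |
| Week 24 scan, dose withheld | Week 20 | 20 + 24 = Week 44 | 24 − 4 = 20 | Weeks 28, 36, 44 |
| Week 32 scan, dose withheld | Week 24 | 24 + 24 = Week 48 | 24 − 8 = 16 | Weeks 32, 40, 48 |
| Just after any dose | t = 0 | last dose + 24 | 24 | last dose + 8, + 16, + 24 |

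Every later 8-weekly scan with the dose withheld also leaves 16 weeks. The planned dose gaps are 1, 2, 4 and 8 weeks, so an unscheduled scan within a gap leaves between 24 weeks and 23, 22, 20 or 16 weeks respectively. The nominal range is 16 to 24 weeks. A 2-week toxicity delay (Section 6.4) in an 8-week gap gives 24 − 10 = 14. Longer delays are possible after discussion with the medical monitor, so 14 is not a floor.

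**Cost of leaving.** Under Section 5.7, a progressed subject who declines the post-treatment period has one End of Study visit. Three visits become one, a net loss of 3 − 1 = 2. This holds for exit before the first post-treatment visit; a later exit loses less.

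Routine adverse event collection runs to End of Study (Section 13), which is 24 weeks after the last dose for a subject who stays. For treatment withdrawn during the treatment period, Table 2, footnote 12, requires recording through 28 days (4 weeks) after the last dose, and Section 13.5 requires the same for SAEs. If that rule covers the early leaver (an assumption), collection runs to the later of exit and 4 weeks, so the loss is 24 − max(t, 4): 20 weeks for t up to 4, and 16 weeks for t = 8. Later SAEs suspected to be related remain reportable (Section 13.5), and clinically significant abnormalities that persist are still followed (Section 9.3).

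**The case against.** The best defence is that a compliant way out exists. The ban ends at End of Study, and Section 5.7 gives a progressed subject who declines the post-treatment period an End of Study visit followed by survival follow-up. The investigator may withdraw a subject for well-being (Section 11.1), and consent can be withdrawn at any time (Section 14.2). Taking a prohibited treatment would be a deviation, but Section 11.2 does not list it as a reason to go off study. All of this stands. A reader might infer that the protocol denies progressed patients treatment or compels them to continue the vaccine; these provisions show that it does neither.

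A second defence is that little is withheld: the Section 7.1 agents stay open, and inclusion criterion 3 says no other standard treatment was available. The first half stands. The second describes entry, when disease was stable or responding. The criterion admits subjects on ongoing first-line targeted or PD-1/PD-L1 therapy, some of whom may have had no chemotherapy. Progression can change the options.

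A third is that subjects off the vaccine show antibody persistence and late toxicity, which new therapy would confound. That is a legitimate aim. It is weakened because the same confounding is accepted in subjects who continue, and because a rule that prompts people to leave loses the very data it would keep clean.

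**Conclusion.** The concern holds in a limited form. As written, Cohort Expansion subjects who stop OBI-833/OBI-821 at progression stay barred from chemotherapy, radiotherapy, surgery and the listed biologics for as long as they remain in post-treatment follow-up, while those who continue are released. The release of radiotherapy and surgery for the latter is an inference from the wording.

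The remaining ban of 16 to 24 weeks assumes progression found during dosing on the nominal schedule. It is shorter after dose delays, or if dosing stopped earlier for another reason. The loss of follow-up is partial, and the number affected, out of at most 14, cannot be known from the protocol.

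A reader might also infer that tumour-response results are compromised by the ban. They are not: subjects who stop have no scheduled scans after progression. No hypothesis is tested (Section 12.1), so the effect on results is descriptive. The case for change rests on patient protection and retention in safety follow-up, at very low cost. It should be corrected by amendment, but it does not threaten the validity of the trial.

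**What to change.** Reword Section 7.2, item 7, and the matching Appendix II line along these lines: *After documented disease progression, any Cohort Expansion subject, whether or not OBI-833/OBI-821 is continued, may receive approved anti-cancer therapy, including radiotherapy and surgery, and remains in scheduled safety and immune follow-up.* Record the start date of each new anti-cancer therapy, so that antibody and safety data after that date can be flagged in summaries and listings.

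The cost is two sentences in an amendment. Section 5.5 already records concomitant medications at every post-treatment visit; radiotherapy and surgery dates need an eCRF entry if none exists. No visits, samples or scans are added. The downside is that post-progression immune and safety data in subjects who stop may be confounded by new therapy, as is already accepted for those who continue.
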